4.4 Consent Procedures

A. Consent Process

Informed consent/assent will be obtained prior to participation. Electronic Consent: Potential participants will be sent a web link where they are presented a document that lists all elements of

informed consent, including: (a) that activities involve research; (b) that participation is voluntary; (c) the purpose, procedures, and duration of the research; (d) any reasonably foreseeable risks, discomforts, and benefits of the research; (e) how confidentiality/privacy will be maintained; (f) circumstances when the investigator may withdraw their participation; (g) how many people will be in the study; (h) incentive for participating; (i) ability to withdraw at any time; (j) that the de-identified data may be shared with other researchers; and (k) name and contact information for Principal Investigator. Consent will be obtained from adults 18 and over and parents/guardians will provide consent for their children if they wish to have them tested. Children age 7 and older will be asked to provide assent in addition to the parental consent. Verbal Consent: Research staff will read the consent document and initial the document. A copy of the consent document will be sent to the participant via email or regular US mail.

B. Waiver or Alteration of Consent Process

- **Waiver or Alteration Details**

N/A

- **Destruction of Identifiers**

Aim 1 and 2 identifiers will be destroyed at the close of the study. Aim 1 data will be de-identified prior to analysis once transcripts have been generated. Aim 1 de-identification of data will consist of removal of all personal identifiers from analytic files and substitution of pseudonyms for participant names. Aim 2 data used for analysis will be fully de-identified upon data export from REDCap and stored on an encrypted, password-protected computer network to which only study investigators and staff have access. De-identification of Aim 2 data will consist of removal of all personal identifiers from analytic files as well as random shifting of dates to preserve participants' anonymity. Audits of REDCap data access will be completed regularly to ensure there is no unauthorized access of REDCap data.

- **Use of Deception/Concealment**

N/A

C. Documentation of Consent

- **Documenting Consent**

For Aim 2 we will provide both electronic and verbal consent options. Electronic Consent: Individuals will receive an electronic survey with a check a box on an electronic consent form agreeing to participate before starting the survey (Aim 2). At the end of the survey, participants must check a box confirming agreement to submit a saliva sample and enter their address where the saliva testing kit will be sent.

- **Waiver of Documentation Of Consent (i.e., will not obtain subject's signature)**

For Aim 1 and Aim 2 verbal consent procedure we are requesting a waiver of documentation of consent. For Aim 1, we will read an information sheet with the elements of consent at the beginning of each virtual zoom focus group (see script uploaded). Those participants who choose to stay in the meeting will be recorded by study staff as providing consent. For Aim 2, we will read the electronic consent at the beginning of the phone call and input the participant's information in the system. For those participants with email, they will receive copies of their consent electronically. For participants without email, a paper of copy of the electronic consent will be mailed.

4.5 Special Consent/Populations

A. Minors-Subjects Who Are Not Yet Adults

Our study population includes healthcare workers, age 18 and over, as well as their household and community members. Children age 4 and older will be included. Children age 7 or greater will provide assent in addition to parental consent. There will be no upper age limit. The parent/legal guardian permission and assent process will follow a similar procedure as outlined above.

Parents/legal guardians with children between age 4 and 18 years will receive an electronic parent permission form before starting the survey with a checkbox providing permission for the child to participate. For children age 7 and older, there will be an electronic assent form with a simplified description of the study procedures and language that offers an option to not participate. Given that this is a minimal risk study and parental/legal guardian permission will be electronically documented, waiver of documentation of assent is requested.

B. Wards of the State

Wards of the state will not be enrolled.

C. Non-English-Speaking Subjects

Spanish

▪ **Process for Non-English-Speaking Subjects**

- Participants who identify Spanish as their preferred language will be recruited. The research team includes individuals who speak Spanish fluently and we will use translated informed consent documents.

▪ **Short Form Consent for Non-English Speakers**

N/A

D. Adults Unable to Consent / Decisionally Impaired Adults

N/A

4.6 Economic Burden and/or Compensation for Subjects

A. Expenses

N/A

B. Compensation/Incentives

Aim 1: We will offer a \$30 gift card incentive to all focus group and key informant interview participants.

Aim 2: We will offer a \$35 Target gift card incentive to all survey/COVID-19 testing participants. Target gift cards were chosen because they can be used for a variety of items for adults and children including the purchase of age appropriate games, toys or books inclusive of shipping costs. A 2004 NAM report on the ethical conduct of clinical research with children describes gift certificates and cash payments ranging from \$10-100 as median incentive amounts for pediatric studies.³⁹

The incentive for Aim 2 is slightly higher than the aim 1 incentive given the additional saliva data collection proposed.

C. Compensation Documentation

For Aim 1 our staff documented the name and address of the participant receiving the card, the cash value of the card, serial number on the card and date of mailing and initialed each entry. For Aim 2, our research staff has identified a gift card management system Rybbon for that interfaces with REDCap and maintains a log that documents distribution of gift cards.

4.7 Risks of Harm/Potential for Benefits to Subjects

A. Description of Risks of Harm to Subjects

This is a minimal risk study, which means that risks from study procedures are similar to those ordinarily encountered in daily life or during the performance of routine physical or psychological examinations or tests. There are no test articles (investigational new drugs, devices, or biologics)

to be used in this study. No risks are anticipated from completion of the virtual focus groups, community conversations, surveys, or self collection of saliva samples. Breach of confidentiality of participants is the main potential risk. However, safeguards are in place at Rutgers University to ensure that confidentiality is maintained through the use of unique study IDs, password protected encrypted computers, and software, as well as other techniques described above. Information is provided to participants regarding the handling and the identification process involved with the data. Information that identifies subjects and subject number will be kept in secure servers. Antivirus software and firewalls are updated regularly to prevent any potential virus infection or hacking attempts. Only study staff that has contact with participants will have access to this information. None of the information being asked would pose any physical, psychological, financial, legal or other risk to participants.

Another potential risk is receipt of a positive COVID-19 test, with potential psychological (e.g., distress) and financial effects (e.g., due to mandatory quarantine on employment). These risks are described in the consent and explained by study personnel prior to enrollment. The protocol poses no other physical, psychological, financial, legal or other risk to participants. The protocol incorporates several steps to minimize all of these risks.

Finally, an additional potential risk may be receipt of an inaccurate test result. Our saliva test was the first saliva-based test to detect SARS-CoV-2 that was granted emergency use authorization by the FDA, and it is the only one authorized for at-home self-collection in the U.S. To date, 200,000 tests have been performed. The test is very sensitive for the presence of SARS-CoV-2, with 98% of tests providing either a positive or a negative result, and only 2% of tests providing an inconclusive result. The test can detect fewer than 10 copies of viral genes per milliliter of saliva, and it can detect the presence of virus in the saliva within 2 days of infection and up to 28 days after infection. Across all known gene sequences of SARS-CoV-2, the test detects the ones in the genes of interest ~100% of the time, making it highly sensitive and specific for those genes. While false positive and false negative rates for this test cannot be calculated currently (the lab does not receive data on what happens to patients after they receive the test), emerging data about false negative rates of saliva-based COVID tests are showing that the false negative rate may be closer to 10%, which is significantly lower than those of nasopharyngeal swab-based tests, which are in the 25-35% range.

B. Procedures which Risk Harm to Embryo, Fetus, and/or Pregnant Subjects

N/A

C. Risks of Harm to Non-Subjects

N/A

D. Assessment of Social Behavior Considerations

N/A

E. Minimizing Risks of Harm

The investigative team will abide by the protocols laid out by our ongoing IRB-approved cohort surveillance studies. All data used for analysis will not contain any PHI. Data will be transferred according to safe data transfer policies utilized by both studies and stored on password protected, encrypted computers. All co-investigators will also sign a confidentiality agreement to prevent both a breach of confidentiality and deductive identification of the de-identified data. All study personnel have been trained in methods of maintaining confidentiality and have passed the Rutgers educational program requirement on the protection of human subjects (CITI training), Good Clinical Practice, and HIPAA regulations at regular intervals. In addition, audit trails, reports for monitoring and other checks will be made to ensure data integrity. These checks will be overseen by the study PIs and research team.

Finally, saliva specimens sent to the lab for analysis will be coded by study ID; no PHI will be provided to these laboratories. The laboratory data will then be merged with other study research data by study ID. These merged files will be securely e-mailed using the study's safe data transfer protocol by the study staff to the study PIs and statisticians for analysis. Again, at no time will PHI be e-mailed or provided to investigators conducting data analysis. Antivirus software and firewalls are updated regularly to prevent any potential virus infection or hacking attempts.

Vault Health, Inc provides administrative and physician services to RUCDR Infinite Biologics for ordering the saliva test, remotely supervising people while they collect their sample (via Zoom video call if needed), and reporting results. When ordering the test, people are asked whether they wish to receive results over email or not. Results are provided within 24-48 hours after the sample is received at the lab. For those who agree to email notification, they receive an email with the test result (positive, negative or inconclusive). Otherwise, they receive an email notification with a link to the results in their Vault account when the results are ready to view. Positive results are communicated via phone by a clinician from Vault, and people are given general CDC recommendations and advised that they need to contact their healthcare provider for follow up care. In the event that participants do not have a primary care provider, they will be referred to an RWJ Barnabas Health Partners provider or a Federally Qualified Health Center (in the case of no insurance) near their residence for follow-up care for COVID symptoms and any psychological distress. Vault reports test results as required by the applicable healthcare government authorities.

F. Potential Benefits to Subjects

The immediate benefit to study participants in Aim 2 is that they will learn if they are SARS-CoV-2 positive or negative. Larger scale benefits to society include potential reduction of transmission through identification of virus-positive individuals. Additional benefits to society are anticipated through the identification of strategies to better engage underserved communities in testing efforts and subsequent COVID-19 vaccination efforts, which can be implemented in NJ and beyond.

5.0 Special Considerations

5.1 Health Insurance Portability and Accountability Act (HIPAA)

The study informed consent provides direct authorization for Vault Health to share COVID testing results and PHI information in the participant's Vault health record with the research team in accordance with this research protocol.

5.2 Family Educational Rights and Privacy Act (FERPA)

N/A

5.3 Code of Federal Regulations Title 45 Part 46 (Vulnerable Populations)

A. Special Populations

Health care employees will be recruited as health care "ambassadors" for this study, however it is solely the individual's choice as to whether or not to participate. No study results will be reported to the employers.

Children will be enrolled in Aim 2 of the study after approval of the appropriate consent/assent forms and data collection instruments. Given that children are susceptible to SARS-CoV-2 infection, this study includes children and their parents as subjects. No greater than minimal risk to participating children is presented in this study. Children will only participate with the permission of their parent or guardian as outlined above. Children age 7 and older will provide assent. Assent would not be developmentally appropriate for younger children.

5.4 General Data Protection Regulation (GDPR)

N/A

5.5 NJ Access to Medical Research Act (Surrogate Consent)

N/A

6.0 Data Management Plan

6.1 Data Analysis

Aim 1

Qualitative data analysis of Zoom transcripts: Data collected will be analyzed to understand and process perspectives of participants' and to adapt and tailor materials and messaging that is meaningful to HCWs, their families, and community participants. Transcripts and fieldnotes will be managed using ATLAS.ti software. Independent data coding will be conducted by 2 team members with discrepancies reviewed at team meetings and resolved through consensus. We will compare and contrast data in the transcripts and fieldnotes within and across stakeholder groups as part of an iterative cycling process of reading, summarizing, and re-reading the data using qualitative interpretive analysis.

Aim 2

Quantitative: To compare participation rates in the two arms, our primary outcome, we will use data on the number of tests performed per month (over the up to 12 month study period). For each intervention, the start time is the date of first attempted contact with potential participants and the end date is either the end of the study period, or the date at which the 1000th individual was tested (whichever comes first). We assume that the number tested follows a Poisson distribution within the time period. We will test the null hypothesis that there is no difference between the two interventions, and also report a 95% confidence interval for the rate ratio. Secondly, we will examine the proportion of tested participants from vulnerable and underserved populations of interest (e.g. Black and Latinx, immigrants, children, and low-income households) in each arm through logistic regression models. We will additionally examine proportion of positive tests in the two study arms to examine whether recruitment through index HCWs taps into more highly exposed participant groups, as hypothesized. To do so we will fit logistic regression models, where the outcome is positive test results (yes/no) and the primary predictor is study arm, adjusting for covariates including participant age, race/ethnicity, sex, occupation, and highest level of educational attainment. Power calculations for this aim are based on the primary outcome measure, testing uptake rate. We report power for rate ratios (RR; ratio of rate in comparison arm relative to intervention arm) of 1.15, 1.2, and 1.3, when expected tests per month in the intervention arm range from 80 to 120 (Table X). We will have about 80% power or greater for RR of 1.15 or greater. To test hypothesis 2B, we will compare participants in the two arms on key characteristics that may be barriers to testing (participant trust, health literacy, English proficiency, and patient activation). We will do so through linear regression models, adjusting for covariates including participant age, race/ethnicity, sex, and highest level of educational attainment.

RR	80	100	120
1.15	0.78	0.82	0.81
1.2	0.94	0.96	0.95
1.3	0.99	0.99	0.99

Cost Analysis: The cost of the intervention components will be calculated using wage rates for personnel at the healthcare organizations and CBOs involved in distribution of materials multiplied by time recorded in time logs. Fringe benefit costs (healthcare, disability, and life insurance) will be added to wages by applying the prevailing fringe benefit rate. The value of time will be calculated as the present value of earnings: (number of hours spent delivering NJ HEROES TOO components) x (interventionist's reported wage rates + fringe benefits). Staff training time will be captured and converted to costs based on application of hourly wage rates. Material costs will include the salivary test, educational print materials provided to study participants, and any other required supplies.

Qualitative/Process Analysis: We will conduct an ongoing mixed methods process evaluation to gather data on how the interventions are implemented while gaining critical insight into factors that influence implementation from multiple perspectives. We will collect quantitative and qualitative data on key intervention components to understand reach, engagement, and adoption of the interventions. Data on reach will assess number of family members/contacts per HCW enrolled. Data on engagement will include data on participation rates for HCWs and families participating across the four counties. Data on adoption will include distribution of educational materials and testing uptake across the four counties. Throughout the intervention, we will purposefully identify and select key informants, individuals with direct experience and knowledge about the intervention, including both those implementing the intervention and recipients of the intervention.

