1.10 Timetable/Schedule of Events

[figure not shown]
The project will be conducted over a 2-year period (See Table below). Start-up activities took ~ 1 month. Aim 1 data collection is complete. Dissemination is ongoing with an abstract accepted for presentation at Academy Health in June 2021, a manuscript under review *at JAMA Open Network* and 3 other manuscripts in development. Aim 2 will be completed by Month 18. Final data analyses, preparation of manuscripts, and final dissemination materials will be completed by Month 24.

MILESTONES AND ACTIVITIES	2020				2021								2022													
	S	O	N	D	J	F	M	A	M	J	J	A	S	O	N	D	J	F	M	A	M	J	J	A		
IRB approvals and revisions	X	X	X	X	X	X	X	X	X	X	X	X	X	X	X	X	X	X	X	X	X	X	X	X	X	
Convene Scientific and Community Advisory Groups	X	X	X	X	X	X	X	X	X	X	X	X	X	X	X	X	X	X	X	X	X	X	X	X	X	
Convene Design Teams	X	X	X	X	X	X	X	X	X	X	X	X	X	X	X	X	X	X	X	X	X	X	X	X	X	
Participate in monthly CDCC cross site meetings/workgroups	X	X	X	X	X	X	X	X	X	X	X	X	X	X	X	X	X	X	X	X	X	X	X	X	X	
Aim 1:																										
Convene Virtual Community Conversations	X	X	X																							
Convene Community Engagement Virtual Salons			X	X	X																					
Conduct rolling qualitative analyses	X	X	X	X	X	X																				
Summarize results and prioritization of messages and strategies	X	X	X	X	X	X																				
Co-design of intervention messaging and materials			X	X	X	X																				
Finalize intervention materials with SmithGifford						X	X																			
Progress reports to CDCC (i.e., barriers and facilitators of COVID-19 testing)	X	X	X	X	X	X																				
Aim 2:																										
HCW and CBO intervention arms						X	X	X	X	X	X	X	X	X	X	X	X	X								
-Intervention activities						X	X	X	X	X	X	X	X	X	X	X	X	X								
-COVID-19 testing and participant data collection						X	X	X	X	X	X	X	X	X	X	X	X	X								
Cost analyses						X	X	X	X	X	X	X	X	X	X	X	X	X								
Process evaluation						X	X	X	X	X	X	X	X	X	X	X	X	X								
-Key informant interviews								X	X	X	X	X	X	X	X	X	X	X								
Progress reports to CDCC (i.e., testing results, barriers and facilitators of COVID-19 testing)						X	X	X	X	X	X	X	X	X	X	X	X	X								
Analysis and Dissemination																										
Manuscript preparation and dissemination						X	X	X	X	X	X	X	X	X	X	X	X	X								

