Recruitment of NJ HEROES TOO arm (Aim 2). In this arm of study aim 2, we will recruit low income health care workers (HCW) employed at several NJ healthcare centers in affected counties to be “ambassadors” to help extend recruitment to their family members and community contacts. We will do so through our two current HCW cohorts, the Rutgers Corona Cohort (RCC) and the Robert Wood Johnson Screening Study (RWJSS) (total Black and Latinx n~1300) which have recruited participants at University Hospital and Robert Wood Johnson University Hospital. Additionally, to increase the reach of our HCW intervention beyond academic medical and healthcare system settings, we have partnered with Parker Health (representing nursing home and assisted living facility HCWs) based in Middlesex county and the Visiting Nurse Association Health Group (VNA), which is a statewide home healthcare organization with significant activities in Essex, Union and Passaic counties. Specifically, the organizations will: (1) inform prospective subjects about the availability of the research (e.g.,

announce the study at meetings with their staff, post links to the study website on their website, on their list serves, in their newsletters and social media); (2) provide prospective subjects with information about the research (i.e., share recruitment materials with their staff); (3) provide prospective subjects from their staff with information about contacting investigators for information or enrollment; and/or (4) ask their staff permission for investigators to contact them.

These approaches leverage trusted relationships (with the HCW), use culturally and linguistically responsive materials, and reduce the burden of testing by using mailed saliva kits to address common barriers encountered by the targeted populations. Campaign materials will also include lists of community resources that can provide support in the event of positive test result, since the potential effects of a positive result and quarantine on employment and a person's ability to meet basic needs are themselves significant barriers. Where applicable (such as in our ongoing cohorts), we will send e-mail blasts/flyers, and place posters and informational kiosks in key hospital and clinical locations. Recruitment materials in English have been developed are part of this protocol amendment. Once they have been approved we will submit Spanish translations for IRB for approval prior to their use.

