Electronic survey data collection: Interested individuals can click active hyperlinks, scan QR codes or type in URLs from recruitment materials to obtain more information on the study and assess their eligibility. Informed consent will be collected electronically after which consented individuals will complete demographic questionnaires about themselves and their households. They will then be asked to extend the invitation to their "spheres of influence" (household and other family members/community contacts) to reach populations who would not otherwise have access to testing. The ambassadors will receive an e-mail and/or text message with an URL link to forward to their contacts. By clicking that link, the household and other family member/community contact will be taken to a webpage with information on NJ HEROES TOO testing, including contact information for study staff.

Telephone data collection: For individuals who are not able to enter their own information electronically, a phone number will be provided for the study. They can use it to reach a research staff member who will consent them, administer the survey by phone and set them up with Vault Health for testing.

Recruitment of the community-based comparison group arm (Aim 2). For the traditional, community based arm of study aim 2, recruitment will be channeled through extant community-based organizations focused on underserved communities in the counties of interest. These partner organizations will advertise the testing opportunity through their preferred standard community outreach channels (e.g. mailings, flyers, community events) as well as through additional multimedia approaches identified and developed during Aim 1. As in the NJ HEROES TOO arm, interested individuals can either opt for electronic or telephone data collection.

C. Subject Screening

▪ Eligibility Criteria

Aim 1: (1) self-identification as Black or Latinx; (2) age 18 or older; and, (3) have access to phone, internet and/or email/text messages; and, (4) ability to speak, understand, and/or read English or Spanish.

Aim 2 Healthcare Workers: (1) self-identification as Black or Latinx; (2) employment at one of the participating health care settings (Parker Health, Robert Wood Johnson University Hospital, University Hospital, Visiting Nurse Association); (3) resident of Union, Passaic, Middlesex, or Essex County, NJ; and, (4) age 18 or older..

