4.3 Number of Subjects

A. Total Number of Subjects

We anticipate a total of 3000 participants will be enrolled across the two study aims.

Aim 1: We recruited 13 groups and 8 individual interviews with stakeholders who identified as Black and/or Latinx (n=111 individuals).

Aim 2: The goal is to enroll approximately 1000 participants in each of the two study arms (N=2000) over a 12 month period.

We are experiencing a high loss to follow-up rate in Aim 2. Though interest, consent rates and survey completion are high there is also a high rate of loss to follow-up. COVID-19 testing is the study outcome and uptake among participants is low. Therefore, we may need to enroll more than 1000 per arm.

B. Total Number of Subjects If Multicenter Study

N/A

C. Feasibility

For Aim 1 and Aim 2 community based organization arm, drawing from long-established relationships and community partners of MPIs [name], [name], and [name] we have engaged 18 community organizations in the design and development of this project. Organizations serve the cities of Newark, Elizabeth, Irvington, Hillside, Caldwell, Paterson, New Brunswick, Perth Amboy, and their surrounding areas. They range in size, scope and focus from faith-based organizations to large social service groups.

For the Aim 2 HCW arm, our current COVID-19 surveillance cohorts include nearly 4000 HCWs, of whom we estimate 32% (n~1300) meet criteria to serve as ambassadors. We anticipate that approximately 1000 more HCWs from Parker Health and the Visiting Nurse Association will be eligible.

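### The primary rate-ratio test and 95% CI assume Poisson variance, although ambassador and household recruitment can make tests arrive in groups; the variance should allow for this clustering.

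*Combined protocol and SAP*

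**What the plan says.** Section 6.1 (Aim 2, Quantitative) compares the arms on tests performed per month. Each arm runs from its own first attempted contact to the end of the study period or its 1000th tested person. On the variance it says only "We assume that the number tested follows a Poisson distribution within the time period". A test of no difference and a 95% CI for the rate ratio follow. Neither 6.1 nor 1.5 mentions overdispersion, a robust variance, or clustering by ambassador or household.

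Section 4.1 describes how tests are generated. In the HCW arm, "The ambassadors will receive an e-mail and/or text message with an URL link to forward to their contacts". The eligibility criteria admit household members and contacts in the HCW arm and also in the community arm. The process evaluation in 6.1 counts family members and contacts per enrolled HCW, but only as a measure of reach. Section 4.4 has each participant "enter their address where the saliva testing kit will be sent".

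**The concern.** A Poisson count has variance equal to its mean, which requires that people come for testing independently of one another. The HCW strategy aims at the opposite: one recruited worker should bring in relatives and contacts. The better it works as intended, the further the count departs from Poisson and the more the planned analysis overstates its certainty.

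The primary conclusion rests on this single test and interval. If tests are grouped, the rate ratio is still estimated correctly, but its interval is too short and a difference between arms is declared too often when there is none.

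**Working it through.** **Inputs from the documents.** 80, 100 or 120 tests per month in the intervention arm; rate ratios of 1.15, 1.2 and 1.3; up to 12 months; a cap of 1000 tested per arm (1.5, 6.1). A two-sided 5% level is inferred from the 95% CI and the null of no difference. I take the HCW arm to be the faster one.

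**Input not in the documents.** L, the mean number of tested contacts per HCW. Assumed range: 0.1 to 2, Poisson distributed.

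**1. The plan's own power figure.** Power = Φ(ln RR / √(1/D1 + 1/D2) − 1.96), where D is the expected number tested, at most 1000. For RR 1.15:
- 80/month: D1 = 80 × 12 = 960 and D2 = 960/1.15 = 835. SE = √(1/960 + 1/835) = 0.0473, so power = Φ(0.1398/0.0473 − 1.96) = 0.84.
- 100 or 120/month: both arms reach 1000. SE = √(2/1000) = 0.0447, so power = 0.88.

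The plan prints 0.78, 0.82 and 0.81. Plain Poisson does not reproduce these. Several unstated settings would, for example a two-sided level of 0.025 or a variance factor of about 1.15 to 1.2. The steps below do not depend on the table.

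**2. Variance under grouping.** If groups arrive independently and a group contributes M tests, the count has variance φ times its mean, with φ = E[M²]/E[M]. For one HCW plus Poisson(L) contacts, E[M] = 1 + L and E[M²] = L + (1 + L)², so φ = 1 + L + L/(1 + L).

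**3. Effect on the planned test.** With equal counts and grouping in the HCW arm only, the true variance of the log rate ratio is f = (1 + φ)/2 times the Poisson value. Type I error = 2(1 − Φ(1.96/√f)).

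| L | φ | f | Type I error |
|---|---|---|---|
| 0.1 | 1.19 | 1.10 | 6% |
| 0.25 | 1.45 | 1.23 | 8% |
| 0.5 | 1.83 | 1.42 | 10% |
| 1 | 2.50 | 1.75 | 14% |
| 2 | 3.67 | 2.33 | 20% |

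True coverage of the nominal 95% CI is 100% minus the last column. As an example, with 1000 tests in each arm and an estimated ratio of 1, the Poisson interval is 0.916 to 1.092. At L = 1 the SE is √(2.5/1000 + 1/1000) = 0.0592, and the correct interval is exp(±1.96 × 0.0592) = 0.891 to 1.123.

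**4. Simulation under the plan's stopping rule** (8,000 runs, 12 months, cap of 1000, no true difference). Rejection was 5.1% without grouping, 14 to 15% at L = 1 and 20 to 21% at L = 2. With the same grouping in both arms it was 21 to 22% and 30 to 31%.

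**5. Cluster-robust variance.** In each arm, Var(log N) is estimated by Σmᵢ²/N², where mᵢ is the number tested in cluster i. If everyone is single, this equals 1/N, the Poisson value, so power stays at 0.84 (80/month, RR 1.15). With L from 0.25 to 2, contact delays averaging up to one month and stable underlying rates, simulated type I error was 4.6 to 5.7% (5,000 replicates).

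**6. Power with the correct variance.** At 80/month and RR 1.15, SE² = φ/960 + 1/835. This gives 0.77, 0.71 and 0.62 at L = 0.25, 0.5 and 1.

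**7. Scheduled outreach.** Independent Poisson counts with fixed monthly means, however unequal, sum to a Poisson total. Simulating fixed monthly patterns with a coefficient of variation (CV) of 10% or 20% gave a type I error of 4.8 to 5.0% for the planned test.

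**The case against.** The strongest objection is that the size is unknown. The documents give neither a group size nor a dispersion estimate. Section 4.3 says "We are experiencing a high loss to follow-up rate in Aim 2" and that uptake of testing is low, so tested contacts per ambassador may be few; at 0.1 the error is only about 6%. This stands. It limits the size of the problem, not its direction.

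A reader might also infer that bursts of outreach break the assumption. The HCW arm says "we will send e-mail blasts/flyers, and place posters and informational kiosks in key hospital and clinical locations", and the comparison arm uses "standard community outreach channels (e.g. mailings, flyers, community events". The documents do not support that inference. A calendar of planned activities changes the rate in a fixed way and leaves the total Poisson (step 7). Only random or correlated group arrivals inflate the variance, and nothing in the documents shows that rates vary at random from month to month.

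For the same reason, month-to-month dispersion should not replace the primary variance. A quasi-Poisson model with arm and calendar-month terms counts fixed arm-specific patterns as noise. Against 0.84 for the Poisson test at RR 1.15, simulated power was 0.52 to 0.69 for fixed patterns with CV 10%, 0.10 to 0.47 with CV 20% (depending on the pattern), and 0.04 when only the HCW arm ramps up from 40 to 120 per month.

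Finally, the printed power lies below the plain Poisson value, so some allowance may have been made at the design stage. None is documented, and it would not change the test and interval described in 6.1.

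**Conclusion.** The concern holds for clustering by ambassador and household. The plan fixes the primary variance at the Poisson value without a safeguard, while its own recruitment design gives a direct route to grouped tests. Type I error is about 6% to 20% for 0.1 to 2 tested contacts per HCW. This assumes Poisson numbers of contacts, grouping in the HCW arm only, equal counts and a two-sided 5% test. Grouping in the community arm as well would raise it further; very few tested contacts would make it negligible.

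The documents do not show that the interval will in fact be too narrow, since that depends on group sizes they do not report. The plan should still be changed, because the correction costs no power when there is no grouping.

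**What to change.** In section 6.1, keep the rate ratio, each arm's planned start and end dates, and all planned counts. Replace the Poisson variance of the log rate ratio by the sum over the two arms of Σmᵢ²/N². Define a cluster as people joined, within an arm, by a recorded ambassador referral or a shared kit address. Count people with no recorded link as single and report their share. Report the Poisson interval beside the cluster-robust one. Use the same coded cluster ID for robust standard errors in the logistic and linear models.

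Create the ID before identifiers are removed; sections 1.9, 4.4 and 6.3 place de-identification at export from REDCap.

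An arm plus calendar-month quasi-Poisson model may be added as a sensitivity analysis only, with a note that fixed arm-specific patterns or ramp-ups count as dispersion and can sharply cut its power.

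Costs: a change of wording and a small data step. Aim 2 enrolment is under way, and section 4.1 does not say that forwarded links identify the ambassador, so some referrals may be unrecoverable for people already tested and the correction may be partial. Where clustering exists the interval is wider, with the loss of power shown in step 6.
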